6.1.3. Analysis Methods

The analysis method for comparisons of each Induction Period LY3074828 dose regimen (300 mg, 100 mg, 30 mg) and placebo for categorical binary efficacy and health outcome variables will be a logistic regression analysis with treatment, geographic region (United States/Outside United States [US/OUS]), and previous biologic therapy (yes/no) using SAS PROC Logistic. Note although geographic region is not a stratification factor, due to its potential impact on outcome, unless otherwise specified, it is included in all logistic regression models. In addition, sensitivity analysis with other covariates for primary endpoint will be conducted using logistic regression (Section 6.2.1).

Logistic regression with a Firth penalized likelihood will be used (see [Appendix 1](#) for simulation study). Firth correction is equivalent to specifying Jeffrey's prior and seeking the mode of the posterior distribution. Roughly, it adds half of an observation to the data set assuming that the true values of the regression parameters are equal to 0. The likelihood function is adjusted by a fixed quantity which reduces the positive bias of small samples. The fixed quantity is a function of the information which goes to 0 as sample size increases. Firth correction can be implemented in PROC Logistic by including *firth* as an option in the model statement. The

odds ratio and the corresponding 95% CIs, as well as the treatment differences and the corresponding 95% CIs, will be reported.

In addition, linear trend tests will be performed for dose-response analysis using all 4 doses (placebo, LY3074828 30 mg, 100 mg and 300 mg). For the first test, all 4 doses will be used and the lower 3 doses will be used for the second test, and the lowest 2 doses will be used for the third test. Under the assumption of monotonic treatment response, the conclusion of trend implies that the highest dose in the test is efficacious.

1. Hypothesis 1: There is no treatment difference in PASI 90 response at Week 16 between LY 300 mg and placebo group
2. Test if there is a monotonic linear trend between the 4 doses
3. Hypothesis 2: There is no treatment difference in PASI 90 response at Week 16 between LY 100 mg and placebo group
4. Test if there is a monotonic linear trend between the 3 doses (LY 100 mg, 30 mg, and placebo)
5. Hypothesis 3: There is no treatment difference in PASI 90 response at Week 16 between LY 30 mg and placebo group.

The analysis method for comparisons of each Induction Period LY3074828 dose regimen (300 mg, 100 mg, 30 mg) and placebo for the continuous efficacy and health outcome variables will be a Mixed effect Model Repeat Measurement (MMRM) analysis when the endpoint is collected at multiple postbaseline visits during a study period, or analysis of covariance (ANCOVA) when the endpoint is collected at one postbaseline visit during a study period, or for sensitivity analyses. When the MMRM model is used, the model will include treatment, geographic region (US/OUS), previous therapy (yes/no), baseline value, visit, and the interaction of treatment-by-visit as fixed factors. When the ANCOVA model is used, the model will include baseline value as a continuous covariate and treatment, geographic region (US/OUS), and previous therapy (yes/no) as fixed factors. For both models, the covariance structure to model the within-patient errors will be unstructured. The Restricted Maximum Likelihood (REML) will be used. The Kenward-Roger method will be used to estimate the denominator degrees of freedom. If the unstructured covariance matrix results in a lack of convergence, the heterogeneous Toeplitz covariance structure, followed by the heterogeneous autoregressive covariance structure, followed by the compound symmetry will be used. This order is specified according to a decreasing number of covariance parameters in the structure. Type III tests for the least squares (LS) means will be used for the statistical comparison; the 95% CI will be reported. Dosing regimen comparisons at Week 16 (Visit 7) and all other postbaseline visits in the Induction Period will be reported.

Proportions and 95% confidence intervals will be summarized for binary outcomes observed in the Maintenance Period. Mean change from baseline and 95% confidence intervals will be summarized for continuous outcomes observed in the Maintenance Period.

The Kaplan-Meier product limit method will be used to estimate the survival curves for post induction (includes Maintenance and Follow-up Periods) time-to-event variables (time to loss of response, time to response recapture after loss of response); median times will be summarized by treatment.

Time to First Loss of Response in the Maintenance Period for PRN Patients

Time to first loss of response (PASI 90 or PASI 100) in the Maintenance Period includes only those subjects who achieved the respective response at Week 16 and is defined in weeks as:

$$(First\ study\ day\ when\ response\ is\ lower\ than\ the\ specified\ level - First\ study\ day\ when\ response\ is\ greater\ than\ or\ equal\ to\ the\ specified\ level + 1) / 7$$

If a patient does not lose response by completion or early discontinuation of the Maintenance Period, the patient will be censored with the censored date defined as the earliest date between the data cutoff for an interim analysis, the study discontinuation date, Maintenance Period end date for non-rescued patients, or the rescue start date.

Time to Recapture of Response in the Maintenance Period After PRN Dosing

Time to recapture of response (for example, PASI 90 or PASI 100) in the Maintenance Period includes only those subjects who lost the specified level of response during the Maintenance Period and is defined in weeks as:

$$(First\ study\ day\ when\ response\ is\ recaptured\ at\ the\ specified\ level - First\ study\ day\ when\ response\ is\ lower\ than\ the\ specified\ level + 1) / 7$$

If a patient does not recapture response by completion or early discontinuation of the Maintenance Period, the patient will be censored with the censored date defined as the earliest date between the data cutoff for an interim analysis, the study discontinuation date, Maintenance Period end date for non-rescued patients, or the rescue start date.

Time to Recapture of Response in the Rescue Period

Time to recapture of response (PASI 50, PASI 90, or PASI 100) in the Rescue Period includes only those subjects who lost the specified level of response during the Maintenance Period and is defined in weeks as:

$$(First\ study\ day\ when\ response\ is\ recaptured\ at\ the\ specified\ level - First\ study\ day\ when\ response\ is\ lower\ than\ the\ specified\ level + 1) / 7$$

If a patient does not recapture response by completion or early discontinuation of the Rescue Period, the patient will be censored with the censored date defined as the earliest date between the data cutoff for an interim analysis, the study discontinuation date, Rescue Period end date, and the start date of the Follow-up Period.

For variables that are not collected at each postbaseline visit, data may exist at visits where the variable was not scheduled to be collected, due to early discontinuation visits. In these situations, data from the early discontinuation visit that do not correspond to the planned

collection schedule will be excluded from the MMRM analysis (Andersen and Millen 2013). However, the data will still be used in other analyses, including shift analyses, change from baseline to mBOCF endpoint analyses, and other categorical analyses.

Fisher's exact test will be used for all adverse events (AEs). The continuous baseline characteristics will be analyzed using an analysis of variance (ANOVA) model with dosing regimen as a factor. Continuous vital sign data and laboratory values will be analyzed by an ANCOVA with dosing regimen and baseline value in the model.

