4.3. Exploratory Objectives

- To characterize the loss of response during the Maintenance Period (if applicable) for subjects who achieve PASI 100 at Week 16
- To characterize the loss of response during the Maintenance Period (if applicable) for subjects who achieve PASI 90 at Week 16
- To characterize the ability of retreatment (if applicable) with LY3074828 to regain PASI 100 for subjects who achieve PASI 100 response at Week 16 and experience loss of response during the Maintenance Period
- To characterize the ability of retreatment (if applicable) with LY3074828 to regain PASI 90 for subjects who achieve PASI 90 response at Week 16 and experience loss of response during the Maintenance Period
- To evaluate the efficacy of treatment with LY3074828 in inducing PASI 100, PASI 90, PASI 75, and mean PASI improvements at all time points evaluated
- To evaluate the efficacy of treatment with LY3074828 in inducing mean BSA improvements at all time points evaluated
- To evaluate the efficacy of treatment with LY3074828 in inducing sPGA 0 and sPGA 0/1 at all time points evaluated

- To evaluate the efficacy of treatment with LY3074828 in PSSI at all time points evaluated
- To evaluate the efficacy of LY3074828 on patient reported outcome measures: Psoriasis Symptom Scale, Patient Global Assessment, DLQI, and SF-36 at all time points evaluated
- To evaluate the psychometric properties of the Psoriasis Symptom Scale including validity, reliability, and responder definition
- To evaluate the relationships between LY3074828 exposure, biomarkers, and efficacy
- To evaluate the development of anti-drug antibodies for LY3074828.

5. Study Design

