5.2. Determination of Sample Size

Approximately 200 subjects will be randomized at a 1:1:1:1 ratio in the blinded induction dosing period to LY3074828 30 mg, 100 mg, 300 mg, and placebo (50 subjects per dosing regimen, respectively). Randomization will be stratified by prior exposure to biologic therapy for psoriasis (yes/no).

Assuming 60% and 3% PASI 90 response rates at 16 weeks for LY3074828 and placebo, respectively, pairwise comparisons to placebo have over 99% power using a 2-sided Fisher's exact test at the 0.05 significance level, with no adjustment for multiple comparisons.

As results for PRN dose arms in the Maintenance Period will support the maintenance dosing strategy in Phase 3 planning, a reasonable total number of subjects who completed 1-3 visits in the Maintenance Period (Week 20 to Week 28) will be needed. Based on study simulations under the treatment effect scenario outlined above, approximately 49 subjects (9 on 30 mg, 18 on 100 mg, 22 on 300 mg PRN arms) will have completed the Week 20 visit at the time of the primary endpoint datalock.

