6.1.2. Definitions

6.1.2.1. Study Time Intervals

Induction Period

All subjects who were randomized to the study are considered as entering the Induction Period.

The start of the Induction Period is defined as the date of first injection following randomization. For subjects who were randomized but not dosed, the Induction Period starts at the randomization date.

The end of the Induction Period is defined as the date of PASI measurement at Week 16, or the early termination date if subjects discontinued from study prior to or at Week 16, or Day 117, whichever comes first.

Maintenance Period

All subjects who had Week 16 visit with PASI measurement (except the ones discontinued the study at Week 16) are considered to have entered the Maintenance Period.

The start of the Maintenance Period is defined as the same date as end of the Induction Period, which is the date of PASI measurement at Week 16.

The end of the Maintenance Period is defined as the visit date at Week 104, or the date when the subjects received rescue treatment, or the early termination date if subjects discontinued from study prior to or at Week 104, whichever comes first.

Rescue Period

All subjects in PRN groups who received at least 1 dose of rescue treatment are considered to have entered the Rescue Period, and will be included in the Rescue Period analysis population.

The start of the Rescue Period is defined as the date the patient received the first dose of rescue treatment.

The end of the Rescue Period is defined as the visit date at Week 104, or early termination date if subjects discontinued from study prior to or at Week 104, whichever comes first.

Follow-up Period

All subjects who had Visit 29 are considered to have entered the Follow-up Period, and will be included in the Follow-up Period analysis population.

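### The SAP 6.1.3 formula for time to first loss of response ties neither of its two dates to the Maintenance Period, so it fails if read literally and, under one plausible repair, counts Induction time as durability

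*SAP*

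**What the plan says.** SAP 6.1.3 introduces the variable under a heading that places the loss in the Maintenance Period and restricts it to PRN patients. It "includes only those subjects who achieved the respective response at Week 16 and is defined in weeks as" the difference of two dates, plus 1, divided by 7. The backslashes in the next two quotes come from the formula's typesetting.

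- The date of loss is "First\ study\ day\ when\ response\ is\ lower\ than\ the\ specified\ level".
- The date subtracted, which is the time origin, is "First\ study\ day\ when\ response\ is\ greater\ than\ or\ equal\ to\ the\ specified\ level".

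The surrounding text points to Week 16 as the origin:

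- SAP 6.1.2.1, referring to the Week 16 assessment: "The start of the Maintenance Period is defined as the same date as end of the Induction Period, which is the date of PASI measurement".
- SAP 4.3, with a matching objective for PASI 100: "To characterize the loss of response during the Maintenance Period (if applicable) for subjects who achieve PASI 90 at Week 16".
- The Kaplan-Meier paragraph in SAP 6.1.3 describes these variables as post-induction, and SAP Table 6.3 gives the Maintenance Period as the time point.

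The Protocol's Schedule of Activities (Section 2) has PASI scored at baseline, at Weeks 2, 4, 8, 12 and 16, and every 4 weeks in Maintenance. Protocol 10.3.1.2 says only that the median time to loss is summarized by treatment. No section states the origin as Week 16. On use, SAP 5.2 says: "As results for PRN dose arms in the Maintenance Period will support the maintenance dosing strategy in Phase 3 planning".

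**The concern.** Membership of the analysis is settled at Week 16, and the stated interest is loss after Week 16. The formula uses neither fact. Its origin is simply the first day in response, which can fall anywhere from Week 2 to Week 16. Its event is simply the first day out of response, which for most subjects is a visit before they had responded at all.

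A programmer must therefore add a restriction that the SAP does not supply. The heading describes the loss, so confining only the loss date to Maintenance is an obvious repair. It leaves the origin in Induction. A subject who had lost response by Week 16 is not in the analysis, so the time from first response to Week 16 cannot contain a counted event. Kaplan-Meier would still treat it as observed time in response.

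Week 16 is also the natural origin by design. PRN subjects are scheduled for doses at Weeks 0 and 8 and are not dosed at Week 16, so a Week 16 clock starts all of them at the same planned interval since the last dose. An origin at first response does not. For a first response at Week 2 or 4 it also counts time before the second dose as durability. At stake is the description of how long response lasts in each PRN arm, and whether arms that differ only in speed of onset would appear to differ in durability.

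**Working it through.** The plan gives no figure for time to loss, so there is none to reproduce. The one planning figure that can be checked is the Week 16 power in SAP 5.2 (60% against 3%, 50 per arm, two-sided Fisher test at 0.05, over 99%). It reproduces at above 99.99% by exact enumeration, but has no bearing here.

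**Inputs.** The formula is (day of loss − day of origin + 1)/7, from SAP 6.1.3. Visit weeks come from Protocol Section 2. Days below are 7 × week; the differences do not depend on the day-numbering convention.

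**Reading 1: both dates literal.** Take a subject below PASI 90 at Weeks 2 and 4, in response from Week 8, and below again at Week 24. The first day below is Week 2 (day 14) and the first day in response is Week 8 (day 56). The time is (14 − 56 + 1)/7 = −5.9 weeks. The only subjects who escape this are those already in response at Week 2, and only if baseline is not counted as a day below the level. Taking the first day below *after* first response does not fully repair it. A subject in response at Week 8, below at Week 12 and back at Week 16 gets (84 − 56 + 1)/7 = 4.1 weeks, an Induction event in someone who enters Maintenance as a responder.

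**Reading 2: loss confined to Maintenance, origin literal.**

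| First response | Loss at Week 24 | Loss at Week 36 | Weeks added before Week 16 |
|---|---|---|---|
| Week 2 | 22.1 | 34.1 | 14 |
| Week 4 | 20.1 | 32.1 | 12 |
| Week 8 | 16.1 | 28.1 | 8 |
| Week 12 | 12.1 | 24.1 | 4 |
| Week 16 | 8.1 | 20.1 | 0 |

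**Reading 3: both dates confined to Maintenance.** Every included subject is in response on the Week 16 date, so that date is the origin. Every row becomes 8.1 weeks (loss at Week 24) or 20.1 weeks (loss at Week 36).

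**Illustration of an arm difference under Reading 2.** The documents give no onset distribution by dose, so both pairs of mixes below are assumptions. The mean added time is the sum of share × (16 − week of first response).

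- Pair A, shares at Weeks 2/4/8/12/16. Earlier onset, 2/15/35/28/20%: 0.02×14 + 0.15×12 + 0.35×8 + 0.28×4 = 6.0 weeks. Later onset, 0/5/20/35/40%: 0.05×12 + 0.20×8 + 0.35×4 = 3.6 weeks. Gap 2.4 weeks.
- Pair B, shares at Weeks 4/8/12/16. Earlier onset, 15/35/30/20%: 0.15×12 + 0.35×8 + 0.30×4 = 5.8 weeks. Later onset, 0/10/30/60%: 0.10×8 + 0.30×4 = 2.0 weeks. Gap 3.8 weeks.

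Pair B was simulated with 200,000 subjects per arm, the same exponential loss after Week 16 in both arms, 4-weekly visits and 88 weeks of Maintenance. Entries are earlier-onset against later-onset arm, in weeks. Means are of recorded times, with subjects still in response censored at the end of Maintenance.

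| Assumed true median | Mean, Week 16 clock | Mean, Reading 2 | KM median, Week 16 clock | KM median, Reading 2 |
|---|---|---|---|---|
| 12 | 19.3 v 19.4 | 25.2 v 21.4 | 12.1 v 12.1 | 20.1 v 16.1 |
| 24 | 34.0 v 33.9 | 39.8 v 35.9 | 28.1 v 24.1 | 32.1 v 28.1 |
| 40 | 46.9 v 46.9 | 52.7 v 48.9 | 40.1 v 40.1 | 48.1 v 44.1 |

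Each assumed median falls exactly on a visit, so the Week 16 median can land on that visit or the next by chance; the 28.1 v 24.1 entry is such a case. The means do not have this problem. They show no difference on the Week 16 clock and about 3.8 weeks under Reading 2.

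**The case against.** The strongest reply is that the heading governs the whole definition. If loss in the Maintenance Period scopes both dates, the origin is the Week 16 assessment for every included subject, and nothing is biased. The post-induction wording, Table 6.3 and the Week 16 entry condition all favour that reading. Upward bias needs a mixed reading, literal for the origin and scoped for the event, and the documents do not show that anyone would program it that way. This stands. A reader might infer that the plan overstates durability in every arm, or that it makes faster-acting doses look more durable. The documents do not support either as a fact: only one of the three readings has that effect, and nothing in them says which dose responds sooner or by how much.

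It is also fair that the analysis is exploratory and descriptive, with no test planned between PRN arms. It would be tempting to call this curve the main output of the PRN design, but SAP 5.2 speaks of PRN results in general, and Protocol 5.4 stresses how often dosing is needed. Other planned outputs do not use this formula: the number of PRN doses (SAP 6.9.3) and PASI response by Maintenance visit with NRI (SAP Table 6.3). A distorted curve could be checked against them.

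The reply does not rescue the text. It works only by adding a restriction to both terms that the formula lacks, and competent programmers could add different ones.

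**Conclusion.** The definition is wrong as written and should be corrected. It conflicts with its own heading, its Week 16 responder population and the SAP's start of Maintenance, and read literally it gives times of zero or less for nearly all subjects.

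The size depends on the repair chosen. With both dates confined to Maintenance there is no error. With only the loss date confined, 0 to 14 weeks are added per subject, Kaplan-Meier medians are inflated, and the inflation is greater in any arm that responds sooner. The per-subject range needs only the visit schedule. The arm gaps of 2.4 and 3.8 weeks illustrate assumed onset mixes and are not estimates for this trial. The primary endpoint is untouched. The point matters because the PRN results are intended to inform Phase 3 maintenance planning.

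**What to change.** For subjects in response at Week 16, define time to first loss as (date of the first PASI assessment after Week 16 with response below the level − date of the Week 16 PASI assessment + 1)/7, separately for PASI 90 and PASI 100. Keep the existing censoring dates, and state that censored times are measured from the same Week 16 origin. If duration from first response is also wanted, report it as a separate, labelled variable and not as loss in the Maintenance Period. The recapture formulas in SAP 6.1.3 start from the same unanchored loss date, so defining that date once would serve them too.

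The cost is a sentence in the SAP and one derivation line, with no new data. Reported durations shorten if the origin would otherwise have been first response, and stay the same if Week 16 was already intended.

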## 8.2. Discontinuation from the Study

Some possible reasons that may lead to permanent discontinuation include:

- enrollment in any other clinical trial involving an investigational product or enrollment in any other type of medical research judged not to be scientifically or medically compatible with this study. **Note:** Enrollment in the separate long-term extension study shall be considered compatible with Study AMAF, provided that the subject is not permanently discontinued from treatment or from the study, and provided that the subject is deemed eligible for enrollment in the separate long-term extension study.
- participation in the study needs to be stopped for medical, safety, regulatory, or other reasons consistent with applicable laws, regulations, and good clinical practice (GCP)
- investigator decision
  - the investigator decides that the subject should be discontinued from the study
  - if the subject, for any reason, requires treatment with another therapeutic agent that has been demonstrated to be effective for treatment of the study indication, discontinuation from the study occurs prior to introduction of the new agent
- subject decision
  - the subject requests to be withdrawn from the study
- AE
  - If the investigator decides that the subject should be withdrawn because of an AE/SAE or a clinically significant laboratory value, the investigational product is to be discontinued and appropriate measures are to be taken. Lilly or its designee is to be alerted immediately. Refer to Safety Evaluations, Sections 9.2 and 9.2.1.
- subject experiences a systemic hypersensitivity event (such as anaphylaxis) following administration of investigational product.
- subject becomes pregnant

Subjects who discontinue the study early will have end-of-study procedures as outlined in Visit 804 in the Schedule of Activities (Section 2).

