## 8.3. Lost to Follow-Up

A subject will be considered lost to follow-up if he or she repeatedly fails to return for scheduled visits and is unable to be contacted by the study site. Site personnel are expected to make diligent attempts to contact subjects who fail to return for a scheduled visit or were otherwise unable to be followed up by the site.

Site personnel, or an independent third party, will attempt to collect the vital status of the subject within legal and ethical boundaries for all subjects randomized, including those who did not get

investigational product. Public sources may be searched for vital status information. If vital status is determined, this will be documented and the subject will not be considered lost to follow-up.

Lilly personnel will not be involved in any attempts to collect vital status information.

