5.1. Summary of Study Design

Study AMAF is a multicenter, randomized, parallel-arm, placebo-controlled trial with 4 study periods in subjects with moderate-to-severe plaque psoriasis.

[figure not shown]
Screening Period (≤4 weeks): Subjects will be evaluated for study eligibility ≤28 days before the baseline visit (Visit 2/Week 0). At the baseline visit (Visit 2), subjects who fulfill the eligibility criteria will be randomized to 1 of 4 induction treatment arms.

Induction Period (16 weeks): A double-blind, 16-week Induction Period is designed to establish the efficacy and safety of LY3074828 administered at Visit 2 (Week 0) and Visit 5 (Week 8). Subjects will be randomized to 1 of 4 induction treatment arms (LY3074828 30 mg SC, LY3074828 100 mg SC, LY3074828 300 mg SC, and placebo every 8 weeks [Q8W]) stratified on the basis of previous exposure to biologic therapy for treatment of psoriasis.

Maintenance Period (88 weeks): The Maintenance Period consists of 88 weeks of treatment. At the end of the Induction Period (Week 16), subjects will continue treatment in the Maintenance Period which is intended to explore 1 of 2 treatment strategies through Week 104. All placebo subjects and subjects assigned to treatment with LY3074828 who have a <90% improvement in Psoriasis Area and Severity Index (PASI) from baseline (PASI 90) at Week 16 will receive LY3074828 300 mg SC Q8W during the entire Maintenance Period. Subjects with ≥PASI 90 PRN dosing group) at Week 16 will only be dosed with LY3074828 at the baseline dose level assignment no more frequently than Q8W when disease activity level is <PASI 90, and this will continue until ≥PASI 90 is regained.

Follow-up Period (16 weeks): The Follow-up Period will include a visit every 4 weeks for a total of 16 weeks following Visit 29 to assess subject safety and study drug efficacy.

[Figure 5.1](#) illustrates the study design.

^a Visits will occur every 4 weeks in the Maintenance and Follow-up Periods.
 Abbreviations: PASI = Psoriasis Area and Severity Index; PRN = as needed; Q8W = every 8 weeks.

Figure 5.1. Illustration of study design for Clinical Protocol I6T-MC-AMAF.

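### Event-free subjects who leave without an early-termination PASI should be censored at their last PASI in the three Kaplan-Meier rules, not at the study discontinuation date

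*SAP*

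**What the plan says.** SAP section 6.1.3 plans Kaplan-Meier curves: "The Kaplan-Meier product limit method will be used to estimate the survival curves for post induction" time-to-event variables, with median times by treatment. The events are falling below, or regaining, a PASI response level.

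All three definitions have event-free subjects "censored date defined as the earliest date between the data cutoff for an interim analysis, the study discontinuation date" and further dates. For loss and recapture in the Maintenance Period the further dates are "Maintenance Period end date for non-rescued patients, or the rescue start date". For recapture in the Rescue Period the list is the interim cutoff plus "the study discontinuation date, Rescue Period end date, and the start date of the Follow-up Period". The last PASI assessment appears in none of them. The period-end dates do not supply it either: under SAP section 6.1.2.1, Maintenance and Rescue end at the early termination date for a subject who leaves the study.

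The figure note in SAP section 5.1 sets the visit interval: "Visits will occur every 4 weeks in the Maintenance and Follow-up Periods". The Protocol Schedule of Activities places PASI at each of these visits, with a window of ±5 days. Protocol section 8.3 counts a subject as lost "if he or she repeatedly fails to return for scheduled visits and is unable to be contacted by the study site". Protocol section 8.2 adds: "Subjects who discontinue the study early will have end-of-study procedures as outlined in Visit 804", and the Schedule lists PASI at that visit.

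**The concern.** A loss or recapture of response can be observed only when PASI is scored. A Kaplan-Meier denominator should hold only subjects in whom an event could be seen at that time. A subject who stops attending, has no termination visit and is declared lost some visits later is counted under the stated rule as at risk and event-free throughout the gap. The error has one direction: the event-free proportion is too high. For loss of response, durability without dosing looks better than it is. For recapture, return to response looks slower.

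The same subject is handled in opposite ways within the SAP. Under section 6.3.1 a missing Maintenance visit is a non-response, while the Kaplan-Meier analysis carries the subject as a continuing responder until discontinuation.

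The curves are exploratory, but SAP section 5.2 says that the PRN results will inform the maintenance dosing strategy for Phase 3, and durability off drug is what a PRN arm shows.

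**Working it through.** **Figures in the plan.** The documents give no event count, median or precision for these analyses, so there is no planned figure to reproduce. The one stated power figure concerns the Week 16 endpoint: over 99% for 60% vs 3% with 50 per arm. It reproduces (Fisher's exact test, 0.9999999) and has no bearing here.

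**Inputs from the documents.** PASI every 4 weeks ±5 days to Week 104; the censoring dates above; loss to follow-up after repeated missed visits. Reading 'repeatedly' as at least two visits gives 2 × 4 = 8 weeks or more from last PASI to declaration.

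**Assumptions, not in the documents.** Exponential time to loss of response with median 24 or 40 weeks; 5, 10 or 20% lost per year, independently of response; gap from last PASI to recorded discontinuation of 0, 8, 16 or 26 weeks.

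**Step 1, hand example.** Take 30 PRN responders (60% of 50). Three are lost after an assessment and recorded as discontinued three visits later. Three losses of response are seen at each of those three visits. With S = product of (1 − d/n):

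- SAP rule: (27/30)(24/27)(21/24) = 21/30 = 0.700
- Last-PASI censoring: (24/27)(21/24)(18/21) = 18/27 = 0.667

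The difference is 3.3 points.

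**Step 2, simulation of loss of response.** 200,000 subjects per scenario, comparing the SAP rule, last-PASI censoring and complete follow-up. Retained response about 36 weeks into Maintenance, true median 40 weeks:

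| Lost per year | Gap (weeks) | SAP rule | Last PASI | Complete | SAP minus last PASI (points) |
|---|---|---|---|---|---|
| 5% | 8 | 0.537 | 0.534 | 0.535 | 0.3 |
| 5% | 16 | 0.539 | 0.534 | 0.535 | 0.5 |
| 5% | 26 | 0.543 | 0.535 | 0.536 | 0.8 |
| 10% | 8 | 0.539 | 0.533 | 0.535 | 0.6 |
| 10% | 16 | 0.545 | 0.535 | 0.536 | 1.0 |
| 10% | 26 | 0.550 | 0.536 | 0.537 | 1.4 |
| 20% | 8 | 0.543 | 0.531 | 0.534 | 1.2 |
| 20% | 16 | 0.559 | 0.537 | 0.540 | 2.2 |
| 20% | 26 | 0.565 | 0.534 | 0.536 | 3.1 |

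With a gap of 0 the first two rules are identical. Over both medians and both time points (36 and 88 weeks), the smallest excess with a gap is 0.062 − 0.061 = 0.1 point (median 24, 5%, 8 weeks, at 88 weeks). The largest is 0.391 − 0.351 = 4.0 points (median 24, 20%, 26 weeks, at 36 weeks).

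I do not use the estimated median as the measure. It can only move from one visit to the next, and in these runs it also flipped under complete follow-up.

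**Step 3, recapture.** A smaller simulation assumed 12 subjects at risk, median 12 weeks, 5 to 10% lost and gaps of 8 to 24 weeks. The not-recaptured proportion at 24 weeks was on average 0.7 to 3.5 points too high. A large-sample rerun agreed in direction and order of size.

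**Step 4, interim cutoff alone.** Nobody lost, cutoff spread over 16 to 52 weeks of Maintenance, estimate at about 36 weeks:

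| True median | SAP rule | Complete | Last PASI for everyone |
|---|---|---|---|
| 40 weeks | 0.535 | 0.535 | 0.515 |
| 24 weeks | 0.353 | 0.353 | 0.331 |

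Cutoff censoring is unbiased for subjects still attending. Last-PASI censoring of everyone is 2.0 and 2.2 points too low. The cause is the visit window: event-free subjects seen early in a window leave the denominator before events later in that window are counted. With visits exactly 4 weeks apart the two rules coincide.

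**The case against.** The strongest reply is that few subjects are affected. Those who withdraw and attend Visit 804/ET have a PASI there, so the two dates roughly coincide. Those who only stop drug remain on the visit schedule (Protocol section 8.1.1). Week 104 is a PASI visit, and assessments precede dosing, so period-end and rescue-start dates need no change. All of this stands, and it confines the point to subjects who leave without a termination PASI.

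Second, the curves are descriptive, with no treatment comparison, and the effect is small beside sampling error: with 30 subjects and S = 0.54, the simple binomial standard error is √(0.54 × 0.46/30) = 0.091, or 9 points. The long-term response rates already count missing data as non-response. This limits the importance of the point, but a one-directional error that one sentence removes is still worth removing.

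Three stronger readings are tempting and are not supported:

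- A reader might infer that the interim cutoff is itself a wrong censoring date. Step 4 shows no bias for subjects still attending. It matters only for those already missing visits but not yet recorded as discontinued.
- A reader might infer that every date should be replaced by the last PASI. That would introduce a downward bias at the interim that exceeds most of the overstatements in the Step 2 table.
- A reader might infer that the recorded date always falls 8 weeks or more after the last PASI. Protocol section 8.3 defines who is lost, not which date is entered, and does not quantify how many visits must be missed. Protocol section 7.6, under which missed dosing visits can lead to discontinuation, could shorten the gap.

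**Conclusion.** The concern holds in a limited form. As written, the three rules keep subjects who leave without a termination PASI in the risk set after their last assessment, whenever the discontinuation date is the date of declaration. Nothing in the documents sets that date back to the last visit. If the sponsor does so in practice, the problem disappears.

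The event-free proportion is then overstated by roughly 0.1 to 4 points. The upper end needs 20% lost per year and a 26-week gap; at 5 to 10% per year and 8 to 16 weeks, the Step 2 table gives 0.3 to 1.0 point. Loss rates, gaps and medians are all assumptions. The primary endpoint and the response-rate summaries are unaffected. This is a minor, worthwhile correction.

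**What to change.** Add one sentence to each of the three rules in SAP section 6.1.3: an event-free subject who is lost to follow-up, or who discontinues the study without a PASI at the early termination visit, is censored at the last non-missing PASI assessment; the same applies to a subject who is already missing scheduled visits at an interim data cutoff. The SAP should define 'already missing' by an explicit visit rule.

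Leave the cutoff, period-end and rescue-start dates in place for subjects still attending. An interval-censored sensitivity analysis could be added but is optional.

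The cost is one extra derivation rule in the time-to-event data set. No data collection, visit or sample size changes.
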